#### 4.5.3.1 Normalization

The treatment dose plan for each lesion treated will be made up of multiple static beams or arcs as described above. For both IMRT and CyberKnife treatments, the apertures are determined by inverse treatment planning. The plan should be normalized to a defined point corresponding closely to the center-of-mass of the PTV (COMPTV). This normalization is used to

select the isodose surface surrounding the target (see below where the exact coverage is stated as 95% of the PTV). Typically, in the case of the gantry mounted treatment units, this point will be the isocenter of the beam rotation; however, it is not a protocol requirement for this point to be the isocenter. For treatment units that do not have a mechanical isocenter, the center-of-mass of the PTV should be used.

Regardless of the treatment unit type, the point identified as COMPTV must have defined stereotactic coordinates and must receive 100% of the normalized dose. Because the beam apertures for the 3D-CRT approach coincide nearly directly with the edge of the PTV (little or no added margin), the external border of the PTV will be covered by a lower isodose surface than usually used in conventional radiotherapy planning, typically around 80% but ranging from 60-90%. For the treatment techniques that use inverse planning algorithms, this same isodose coverage must be achieved. The prescription dose will be delivered to the margin of the PTV (as defined below) and fulfill the requirements below. As such, a “hotspot” will exist within the PTV centrally at the COMPTV with a magnitude of the prescription dose times the reciprocal of the chosen prescription isodose line (i.e., 60-90%).

#### 4.5.3.2 Tissue Density Correction (Tissue Heterogeneity)

For purposes of dose planning and calculation of monitor units for actual treatment, approved corrections for tissue heterogeneity must be used. Examples of appropriate tissue density heterogeneity correction algorithms include properly commissioned superposition/convolution (collapsed cone), AAA, and Monte Carlo. Simple pencil beam and Clarkson algorithms that account for attenuation but not scatter will not be allowed.

#### 4.5.3.3 Composite Planning Dosimetry

While a successful strategy of iterative treatment planning on a per lesion basis is typically carried out in practice when optimizing dosimetry, overall treatment appropriateness and compliance will be judged based on the composite treatment plan summarizing the effects of all beams to all lesions treated simultaneously in absolute (not percentage) dose. This is required even if different lesions are treated on different days. Only composite plans will be submitted for quality assurance. An exemption will be if large (more than 40 cm) cranio-caudal distances separate two adjacent lesions where scanning a common dataset for planning might be problematic (e.g., tube over-heating). In this case, two separate planning data sets will be submitted without a composite plan.

#### 4.5.3.4 Successful Treatment Planning

Successful treatment planning **for each lesion treated** will require accomplishment of all 7 of the following criteria:

##### 1. Normalization

The treatment plan should be normalized such that 100% corresponds to the center of mass of the PTV (COMPTV) receiving the highest dose on protocol.

##### 2. Prescription Isodose Surface Coverage

The prescription isodose surface will be chosen such that 95% of the target volume (PTV) is conformally covered by the prescription isodose surface selected for that lesion and 99% of the target volume (PTV) receives a minimum of 90% of the prescription dose selected for that lesion.

##### 3. Target Dose Heterogeneity

The prescription isodose surface selected in number 2 (above) must be  $\geq 60\%$  of the dose at the center of mass of the PTV (COMPTV) and  $\leq 90\%$  of the dose at the center of mass of the PTV (COMPTV). The COMPTV corresponds to the normalization point (100%) of the plan as noted in number 1 above.

##### 4. High Dose Spillage

a) Location: Any dose  $> 105\%$  of the prescription dose selected for that lesion should occur primarily within the PTV itself and not within the normal tissues outside the PTV. In addition for the PTV receiving the highest dose in the plan, the cumulative volume of all tissue outside the PTV receiving a dose  $> 105\%$  of the highest prescription dose should be no more than 15% of

the size of the PTV volume receiving the highest dose.

b) Volume: Conformality of PTV coverage will be judged such that the ratio of the volume of the prescription isodose meeting criteria 1 through 4 to the volume of the PTV is ideally < 1.2. These criteria will not be required to be met in treating very small tumors (< 2.0 cm axial GTV dimension or < 1.0 cm craniocaudal GTV dimension) in which the required minimum field size of 3.0 cm results in the inability to meet a conformality ratio of 1.2.

#### 5. Intermediate Dose Spillage

The falloff gradient beyond the each PTV extending into normal tissue structures must be rapid in all directions and meet the following criteria:

a) Location: The maximum total dose over all 3 fractions in Gray (Gy) to any point 2 cm or greater away from the PTV in any direction must be no greater than D2cm where D2cm is given by the tables below.

b) Volume: The ratio of the volume of the 50% isodose volume (50% of the prescription dose for the treated lesion) to the volume of the PTV must be no greater than R50% where R50% is given by the table below.

Ratio of 50% Isodose Volume to the PTV, R50%		Maximum Dose at 2 cm from PTV in any direction as % of prescribed dose (Px D). D2cm (Gy) = % x Px D		PTV Volume (cc)
Deviation		Deviation		
none	acceptable	none	acceptable	
<5.9	<7.5	<50.0	<57.0	1.8
<5.5	<6.5	<50.0	<57.0	3.8
<5.1	<6.0	<50.0	<58.0	7.4
<4.7	<5.8	<50.0	<58.0	13.2
<4.5	<5.5	<54.0	<63.0	22.0
<4.3	<5.3	<58.0	<68.0	34.0
<4.0	<5.0	<62.0	<77.0	50.0
<3.5	<4.8	<66.0	<86.0	70.0
<3.3	<4.4	<70.0	<89.0	95.0
<3.1	<4.0	<73.0	<91.0	126.0
<2.9	<3.7	<77.0	<94.0	163.0

Note 1: For values of PTV dimension or volume not specified, linear interpolation between table entries is required.

Note 2: Institutions are encouraged to stay within the values listed as "none" in the table above so that the treatment plan is considered to be per protocol. It is recognized that some treatment planning situations might be more challenging and fall outside these limits, so staying within the values listed as "acceptable" is also permitted. Protocol deviations greater than listed here as "acceptable" will be classified as "unacceptable" for protocol compliance.

Note 3: For tumors within 2 cm of the skin, it may be difficult to meet the values for D2cm and R50. In these cases, these criteria will not be used.

#### 6. Adherence to Critical Organ Dose-Volume Limits

Attempts should be made to meet or be better than the normal tissue constraints listed below while observing the treatment planning priorities listed in Section 5.7.

#### 7. Conducting planning with respect to the planning priorities (Section 5.7)

### 4.6 Planning Priorities

#### 4.6.1 Overall Strategies

Successful treatment planning criteria are listed in the previous section. In general, attempts should be made to successfully satisfy all of the criteria without deviation. In some circumstances, improvements can be made to the dosimetry plan beyond simply meeting the specified goals. In other circumstances, clinicians are faced with the prospect of not ideally meeting one or more of the criteria (i.e., accepting an acceptable deviation). In this section, we provide priorities in which a most ideal plan for protocol purposes is realized. Suggested priority of planning goals in order of importance is:

1. Respect spinal cord, cauda equine and sacral plexus dose constraints.

2. Meet dose “compactness” constraints including the prescription isodose surface coverage, high dose spillage (location and volume), and intermediate dose spillage (D2cm, and R50) as these define the “essence” of SABR.

3. Meet critical structure constraints other than those listed in 1.

The organ constraints are last in priority (except for nervous system tolerance), because they are the least validated. The “essence” of a stereotactic plan is captured mostly in the dose compactness justifying their higher priority. As an example in a case where not all goals can be met, it would be suggested to meet dose compactness goals without deviation even at the expense of a non-spinal cord normal tissue having acceptable deviation. Unacceptable deviations should be avoided in all cases. Again, these are suggested planning priorities and clinicians must use their judgment and experience in actual treatment given the variability of patient presentation and tolerance.

As an example, in some cases a target abuts a normal tissue structure with an assigned constraint. Obviously, it would be impossible to utilize the required expansions, treat to 54 Gy PTV dose, and also meet the normal tissues maximum dose constraint. With the exception of the spinal cord, the protocol allows an “acceptable” deviation such that the abutting normal tissue is allowed a maximum point dose of 105% of the prescription dose; however, the volume constraint must still be respected. As such, the dosimetry might be manipulated by falloff dose polarization so that the compactness criteria are met with an “acceptable” deviation of normal tissue constraints.

[figure not shown]
#### 4.6.2 Specific Strategies

Tumors very near or abutting serially functioning normal structures (e.g., esophagus, great vessels, etc.) make it difficult to meet normal tissue constraints while giving compliant target dose coverage. PTV expansions may cross into adjacent normal tissues confounding the ability to respect the constraint. The planning priorities listed in the previous section must be respected. In cases where a higher priority takes precedence over a normal tissue constraint, attempts should non-the-less be made to spare as much high and intermediate dose to the normal tissue as possible. Specifically, since the prescription dose in each arm is only required to cover 95% of the PTV volume, the 5% not fully covered by the prescription dose can be purposefully manipulate to anatomically occur in the vicinity of a critical normal structure or in the portion of a PTV/normal tissue overlap. While 90% of the prescription dose must still cover the target, this allows the planner to at least lower the maximum dose to the adjacent structure to around 90% of the prescription dose with corresponding lowering of dose fall-off as well. This strategy potentially used for non-spinal cord serial tissues is depicted in the following figure (note: respecting the spinal cord constraints takes precedence over all priorities).

# Abutting Targets/Serial Structures

Subvolume A: Try to strictly meet organ limits (e.g., using IMRT)

Subvolume B: Max dose no more than 90% of script dose

**\* Does NOT apply to spinal cord!**

## 4.7 Critical Structures

### 4.7.1 Critical Structure Dose-Volume Limits

The following tables list dose limits to a point or volume within several critical organs/tissues for a variety of total fractions. **For the spinal cord, these are absolute limits, and treatment delivery that exceeds these limits will constitute a major protocol violation.** For the non-spinal cord tissues, acceptable deviation allows a maximum point dose no more than 105% of the prescription dose for structures within 1 cm of a PTV target while fully respecting the defined volume constraint (for serial tissues) OR exceeding the parallel tissue critical volume dose maximum by no more than 5%. Unacceptable deviation exceeds the volume constraint for serial tissues, exceeds the maximum point dose for serial tissues by more than 105% of the prescription dose, or exceeds the parallel tissue critical volume dose maximum by more than 5%.

The normal tissue constraints listed in the following table list **total dose** for a specified total number of fractions. Participating centers are encouraged to observe prudent treatment planning principles in avoiding unnecessary radiation exposure to critical normal structures irrespective of these limits.

#### Three Fractions

Serial Tissue	Volume	Volume Max (Gy)	Max Point Dose (Gy)**	Endpoint (≥Grade 3)
Spinal Cord	<0.35 cc <1.2 cc	15.9 Gy 13 Gy	22.5 Gy	myelitis
Cauda Equina	<5 cc	21.9 Gy	25.5 Gy	neuritis
Sacral Plexus	<5 cc	22.5 Gy	24 Gy	neuropathy
Esophagus*	<5 cc	17.7 Gy	25.2 Gy	stenosis/fistula
Heart/Pericardium	<15 cc	24 Gy	30 Gy	pericarditis

Great vessels	<10 cc	39 Gy	45 Gy	aneurysm
Rib	<5 cc	40 Gy	50 Gy	Pain or fracture
Skin	<10 cc	31 Gy	33 Gy	ulceration
Stomach	<5 cc	22.5 Gy	30 Gy	ulceration/fistula
Bile duct			36 Gy	stenosis
Duodenum*	<5 cc <10 cc	15.6 Gy 12.9 Gy	22.2 Gy	ulceration
Jejunum/Ileum*	<30 cc	17.4 Gy	27 Gy	enteritis/obstruction
Colon*	<20 cc	24 Gy	34.5 Gy	colitis/fistula
Ureter			40 Gy	stenosis
Renal hilum/vascular trunk	15 cc	19.5 Gy		malignant hypertension
Parallel Tissue	Critical Volume (cc)	Critical Volume Dose Max (Gy)		Endpoint (≥Grade 3)
Lung (Right & Left)	1500 cc	10.5 Gy		Basic Lung Function
Lung (Right & Left)	1000 cc	11.4 Gy	V-11Gy<37%	Pneumonitis
Liver	700 cc	17.1 Gy		Basic Liver Function
Renal cortex (Right & Left)	200 cc	15 Gy		Basic renal function

\*Avoid circumferential irradiation

\*\* "point" defined as 0.035cc or less

#### Four Fractions

Serial Tissue	Volume	Volume Max (Gy)	Max Point Dose (Gy)**	Endpoint (≥Grade 3)
Spinal Cord	<0.35 cc <1.2 cc	18 Gy 14.6 Gy	25.6 Gy	myelitis
Cauda Equina	<5 cc	26 Gy	28.8 Gy	neuritis
Sacral Plexus	<5 cc	26 Gy	28 Gy	neuropathy
Esophagus*	<5 cc	18.8 Gy	30 Gy	stenosis/fistula
Heart/Pericardium	<15 cc	28 Gy	34 Gy	pericarditis
Great vessels	<10 cc	43 Gy	49 Gy	aneurysm
Rib	<5 cc	43 Gy	54 Gy	Pain or fracture
Skin	<10 cc	33.6 Gy	36 Gy	ulceration
Stomach	<5 cc	25 Gy	33.2 Gy	ulceration/fistula
Bile duct			38.4 Gy	stenosis
Duodenum*	<5 cc <10 cc	17.2 Gy 14 Gy	24.4 Gy	ulceration
Jejunum/Ileum*	<30 cc	18.8 Gy	30 Gy	enteritis/obstruction
Colon*	<20 cc	26 Gy	37.2 Gy	colitis/fistula
Ureter			43 Gy	stenosis
Renal hilum/vascular trunk	15 cc	21.5 Gy		malignant hypertension
Parallel Tissue	Critical Volume (cc)	Critical Volume Dose Max (Gy)		Endpoint (≥Grade 3)
Lung (Right & Left)	1500 cc	11.6 Gy		Basic Lung Function
Lung (Right & Left)	1000 cc	12.4 Gy	V-13Gy<37%	Pneumonitis
Liver	700 cc	19.2 Gy		Basic Liver Function

Renal cortex (Right & Left)	200 cc	17 Gy		Basic renal function

\*Avoid circumferential irradiation

\*\* "point" defined as 0.035cc or less

#### Five Fractions

Serial Tissue	Volume	Volume Max (Gy)	Max Point Dose (Gy)**	Endpoint (≥Grade 3)
Spinal Cord	<0.35 cc <1.2 cc	22 Gy 15.6 Gy	28 Gy	myelitis
Cauda Equina	<5 cc	30 Gy	31.5 Gy	neuritis
Sacral Plexus	<5 cc	30 Gy	32 Gy	neuropathy
Esophagus*	<5 cc	19.5 Gy	35 Gy	stenosis/fistula
Heart/Pericardium	<15 cc	32 Gy	38 Gy	pericarditis
Great vessels	<10 cc	47 Gy	53 Gy	aneurysm
Rib	<5 cc	45 Gy	57 Gy	Pain or fracture
Skin	<10 cc	36.5 Gy	38.5 Gy	ulceration
Stomach	<5cc	26.5 Gy	35 Gy	ulceration/fistula
Bile duct			41 Gy	stenosis
Duodenum*	<5 cc <10 cc	18.5 Gy 14.5 Gy	26 Gy	ulceration
Jejunum/Ileum*	<30 cc	20 Gy	32 Gy	enteritis/obstruction
Colon*	<20 cc	28.5 Gy	40 Gy	colitis/fistula
Ureter			45 Gy	stenosis
Renal hilum/vascular trunk	15 cc	23 Gy		malignant hypertension
Parallel Tissue	Critical Volume (cc)	Critical Volume Dose Max (Gy)		Endpoint (≥Grade 3)
Lung (Right & Left)	1500 cc	12.5 Gy		Basic Lung Function
Lung (Right & Left)	1000 cc	13.5 Gy	V-13.5Gy<37%	Pneumonitis
Liver	700 cc	21 Gy		Basic Liver Function
Renal cortex (Right & Left)	200 cc	18 Gy		Basic renal function

\*Avoid circumferential irradiation

\*\* "point" defined as 0.035cc or less

#### 4.7.2 Contouring of Critical Structures

Critical structure contours will be drawn in axial planes of the primary planning dataset. In general, critical structures should be contoured if they are found within an axial slice within 10 cm in the craniocaudal direction of any PTV slice treated on protocol. As such, they may be further than 10 cm direct separation and still required to be contoured. If a named critical structure is further than 10 cm from any PTV, then it need not be contoured or submitted.

##### Spinal Cord

The spinal cord will be contoured based on the bony limits of the spinal canal. The spinal cord should be contoured starting at least 10 cm above the superior extent of any PTV and continuing on every CT slice to at least 10 below the inferior extent of any PTV. **NOTE: For the spinal cord, constraints are absolute limits, and treatment delivery that exceeds defined limits will constitute a major protocol violation.**

**Cauda Equina**

Starting at the conus (end of spinal cord, typically around L1 or L2) include the entire spinal canal into the sacrum to the filum.

**Esophagus**

The esophagus will be contoured using mediastinal windowing on CT to correspond to the mucosal, submucosa, and all muscular layers out to the fatty adventitia. The esophagus should be contoured starting at least 10 cm above the superior extent of any PTV and continuing on every CT slice to at least 10 below the inferior extent of any PTV.

**Sacral Plexus**

Include the nerve roots from L5 to S3 on each side from the neuroforamina to the coalescing of the nerves at the obturator internus muscle.

**Heart**

The heart will be contoured along with the pericardial sac. The superior aspect (or base) for purposes of contouring will begin at the level of the inferior aspect of the aortic arch (aorto-pulmonary window) and extend inferiorly to the apex of the heart.

**Whole Lung**

Both the right and left lungs should be contoured as one structure. Contouring should be carried out using pulmonary windows. All inflated and collapsed lung should be contoured; however, gross tumor (GTV) and trachea/ipsilateral bronchus as defined above should not be included in this structure.

**PTV + 2 cm**

As part of the QA requirements for "low dose spillage" listed above, a maximum dose to any point 2 cm away in any direction is to be determined (D2cm). To facilitate this QA requirement, an artificial structure 2 cm larger in all directions from the PTV is required. Most treatment planning systems have automatic contouring features that will generate this structure without prohibitive effort at the time of treatment planning. If possible this structure should be constructed as a single contour that is 2 cm larger than the PTV.

**Skin**

The skin will be defined as the outer 0.5 cm of the body surface. As such it is a rind of uniform thickness (0.5 cm) which envelopes the entire body in the axial planes. The cranial and caudal surface of the superior and inferior limits of the planning CT should not be contoured as skin unless skin is actually present in these locations (e.g., the scalp on the top of the head).

**Rib**

Ribs within 5 cm of the PTV should be contoured by outlining the bone and marrow. Typically, several portions of adjacent ribs will be contoured as one structure. Adjacent ribs, however, should not be contoured in a contiguous fashion (i.e., do not include the inter-costal space as part of the ribs).

**Stomach**

The entire stomach and its contents should be contoured as a single structure as a continuation of the esophagus and ending at the first part of the duodenum.

**Duodenum**

The wall and contents of the 1st, 2nd, and 3rd parts of the duodenum will be contoured as one structure beginning where the stomach ends and finishing as the superior mesenteric artery crosses over the third part of the duodenum.

**Jejunum/Ileum**

As a conglomerate of bowel loops within the abdomen distinguished from stomach, duodenum,

and colorectum.

**Colon**

From the ileocecal area to include the ascending, transverse, descending and sigmoid colon as one structure.

**Renal Hilum**

The collecting system of calyces within the kidney to the pelvis of the kidney and proximal ureters

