Radiation induced renal complications can be slow and non-inflammatory. The extent of radiation induced kidney damage is related to the volume of renal parenchyma receiving radiotherapy, total dose given to the kidney, dose per treatment, and other underlying medical conditions such as diabetes and hypertension. Acute radiation nephritis can be seen months after exposure to radiotherapy [48]. The clinical symptoms related to acute radiation nephritis include hypertension, edema, proteinuria, anemia, and uremia. In standard fractionated treatment to both kidneys about 50% of the patients will develop the clinical manifestation described above a dose of 23 Gy [49]. Among the clinical symptoms, the development of hypertension is the most important prognostic sign correlated with severe morbidity and death. However, when 50% or less of a single kidney is irradiated to a high dose (>26 Gy), clinical radiation induced nephropathy is rare [49].

In this phase II trial, the volume of high dose radiotherapy (>10 Gy) will be restricted to <50% of the entire kidney. The current study will also implement fractionated stereotactic radiosurgery to treat a unilateral kidney tumor. Fractionated radiotherapy is advocated to further reduce the potential toxicity arising from a large single fraction regimen. In fact, fractionated radiotherapy has been the standard treatment for many tumors in variety of locations to reduce the toxicity associated with radiotherapy. A fractionated stereotactic regimen has the potential to reduce the normal tissue toxicity that often accompanies radiotherapy.

Successful implementation of stereotactic radiosurgery of renal tumors may become an effective and the least invasive treatment modality. This study will refine the current understanding of the image guided conformal therapy to the kidney using stereotactic body radiotherapy.

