**Other Structures**

The constraints tables above contain other structures. These are required if the structure is within 10 cm of the PTV.

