### **4.8.2 Contouring Compliance**

Accurate and appropriate contouring is essential for the generation of dose volume statistics. In addition, it is the desire of the investigator to compile a comprehensive database of dose volume information coupled with outcomes data (control/toxicity) in order to define accurate dose response effects. As such, we require that the tumor targets and normal tissues in the vicinity be contoured in all patients. In particular, any structure listed with a constraint in Critical Structures and residing within 10 cm in any direction from the PTV must be contoured. Appropriateness of contouring will be scored by the study PIs as either no deviation, minor deviation, or major deviation.

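### The dose limit for the renal hilum and vascular trunk is paired with a contour definition that lists only urinary structures and names no renal vessel (minor planning-safety correction)

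*Protocol*

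**What the plan says.** The three tables in Section 4.7.1 each carry a serial-tissue row "Renal hilum/vascular trunk". The volume is 15 cc in all three. The dose is 19.5 Gy for three fractions, 21.5 Gy for four and 23 Gy for five. The endpoint is malignant hypertension, and the maximum point dose column is empty.

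Section 4.7.2 tells planners how to draw each structure. Its entry for this row is headed Renal Hilum and reads in full: "The collecting system of calyces within the kidney to the pelvis of the kidney and proximal ureters".

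The closing entry of Section 4.7.2, Other Structures, says of further structures in the tables: "These are required if the structure is within 10 cm of the PTV". Section 4.8.2 makes contouring mandatory for any constrained structure within 10 cm of the PTV and adds: "Appropriateness of contouring will be scored by the study PIs as either no deviation, minor deviation, or major deviation".

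**The concern.** The table row names two things, the hilum and the vascular trunk, and gives them one limit. The drawing instruction covers the calyces, the renal pelvis and the proximal ureters, all of them urinary. A contour that obeys the instruction to the letter leaves out a tissue that the row names.

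The possible consequence is a safety check made on the wrong volume. The row's endpoint, malignant hypertension, is a grade 4 kidney effect in the late-toxicity scale of Appendix C. Section 1.3, writing of radiation nephritis, says: "Among the clinical symptoms, the development of hypertension is the most important prognostic sign correlated with severe morbidity and death". There is also a smaller data-quality consequence. Section 4.8.2 wants a database that links dose-volume figures to outcome, and figures for this row would not be comparable if some planners include the vessels and others do not.

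**Working it through.** There is no figure in the plan to reproduce. The check sets the constraint rows beside the contour definitions.

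1. **Is there another definition of the vessels?** I read every entry in Section 4.7.2. None mentions a renal artery, a renal vein or a vascular trunk. The Renal Cortex entry explicitly leaves the hilum out. Great vessels is a separate table row (less than 10 cc at 39, 43 or 47 Gy) with aneurysm as its endpoint, and it has no contour entry of its own.

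2. **How are the other double-named serial rows treated?** Each table has three.
   - Heart/Pericardium: the Heart entry says "The heart will be contoured along with the pericardial sac", so both halves are covered.
   - Jejunum/Ileum: the entry carries both names in its heading and begins "As a conglomerate of bowel loops within the abdomen", so both halves are covered.
   - Renal hilum/vascular trunk: the heading drops the second half and the text lists only urinary structures, so one half is covered.

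3. **Is this just missing detail?** No. The Great vessels and Ureter rows have no definition at all, and a planner must rely on anatomy and the catch-all clause. Here a definition is given, and it is narrower than the structure being constrained. A planner has positive text to follow, and following it gives a contour without vessels.

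4. **Does the catch-all clause cure it?** It requires structures to be drawn but defines none of them. The tables give hilum and trunk a single 15 cc. A planner who drew the vessels as a separate structure would still not be told whether to add them to that 15 cc.

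5. **Does the contour matter to the result?** For this row, yes. With no maximum point dose, the volume limit is its only test. Sections 4.7.1 and 4.8.1 class a breach of a serial tissue's volume constraint as an unacceptable deviation, and Section 4.6.1 asks that such deviations be avoided in every case. Whether the vessels are counted can therefore, in principle, change how a plan is classified.

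**The case against.** The best reply is that the protocol already requires the trunk to be drawn. It is named in a constraint row, Section 4.8.2 makes every such structure within 10 cm mandatory, and the study PIs score the contours. An experienced planner reading the row label would probably include the vessels. This stands as a reason why omission is unlikely. It does not remove the mismatch, because a contour that matches the written definition could fairly be scored as having no deviation.

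A second reply is that organ limits carry little weight here: "The organ constraints are last in priority (except for nervous system tolerance), because they are the least validated". The priorities are described as suggestions subject to clinical judgement. Kidney tissue also has separate protection, through the 200 cc renal cortex limit and the rule in Section 1.3 that less than half of the kidney may receive more than 10 Gy. This also stands, and it is why the point is minor.

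Three stronger readings are tempting, and the protocol does not support them.

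- **That omitted vessels would put patients at a known added risk of malignant hypertension.** The link from vessels to that endpoint is inferred from the row label. Section 1.3 relates kidney damage to parenchymal volume, total dose, dose per treatment and other illness, and does not mention renal vessels.
- **That each omitted cc of vessel above the limit dose is worth 6.7% of the limit.** This is only 1/15 = 6.7%, which would hold for any tissue left out. It is not an effect size. It also assumes that 15 cc is a ceiling, although this row lacks the less-than sign that the other serial rows with a volume carry.
- **That delivered plans were wrong and need re-checking for safety.** Nothing shows that any plan left the vessels out, and re-checking a delivered plan protects no one already treated.

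**Conclusion.** The point holds as a minor error of wording in treatment planning. The constrained structure and its only contour definition do not match, and no other text in the protocol reconciles them.

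No figure for the size of the effect can be given, because the protocol states neither vessel volumes nor vessel doses. The textual mismatch is certain. That it would change any plan is only a possibility, and it depends on a planner following the definition literally and on the vessels lying within the dose region that the limit addresses.

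The primary endpoint, the sample size of 16 and the power statements in Section 9.2 are unaffected.

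**What to change.** In Section 4.7.2, retitle the Renal Hilum entry to match the table row (Renal hilum/vascular trunk) and state that the contour also includes the renal artery and vein at the hilum. The protocol does not say how far along the vessels the trunk runs, so the study radiation oncologists should confirm the extent. The rest of the definition, including the proximal ureters, can stay. Apply the new wording to all plans from then on.

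Recontouring stored plans is optional. It would serve only the dose-volume database, and would involve at most the 16 planned patients.

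The cost is one line of protocol text. The downside is that, if 15 cc is read as a ceiling, a larger contour can only add to the volume counted, so the limit may be slightly harder to meet.
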